9.4.2 ANALYSIS OF THE PRIMARY EFFICACY ENDPOINT(S)

Phase 2b: Primary efficacy endpoint is change in D-dimer level from Baseline to Day 8, or day of discharge if prior to Day 8. The change in D-dimer will be calculated using proportional change in D-dimer level from the level at baseline to the level at either Day 8 or discharge if discharge occurs before Day 8. A Wilcoxon rank sum test will be performed to compare baseline and Day 8 (or early discharge) D-dimer levels within each treatment group. A second Wilcoxon rank sum test will be used to compare proportional change from baseline to Day 8 (or early discharge) between treatment groups. The primary analysis will involve a comparison of the pooled rNAPc2 treatment groups against the heparin treatment group. Secondary and sensitivity analyses of the primary endpoint will be conducted as described in the statistical analysis plan.

Because the optimal dose rNAPc2 is unknown and its determination is a key objective of the Phase 2b study, the assumption that both doses will be effective and thus can be pooled for statistical analysis may not be correct. Therefore, a series of secondary analyses will be conducted, consisting of analysis for dose response, effectiveness in a single dose group, effectiveness that is related to the extent of baseline D-dimer elevation, and the subgroup analyses described in [Section 9.4.7 SubGroup Analyses](#).

Missingness within the data is to be expected. Subject profile, mortality, or early discharge give rise to the possibility that nonrandom attrition may bias the point estimate for the treatment effect for the primary endpoint. Therefore, missingness will be handled by multiple imputation during a sensitivity analysis as described in the Statistical Analysis Plan (SAP).

Phase 3: The primary efficacy endpoint is time to recovery by Day 30, with day 1 being the date of randomization. Recovery is defined as the first day a participant meets criteria for category 6, 7 or 8 of the ACTT ordinal scale. The analysis of the primary efficacy endpoint will be a comparison of the two treatment groups by a stratified log-rank test, where stratification is according to local laboratory screening D-dimer level $>$ or $\leq 2X$ local laboratory ULN. Cumulative incidence by treatment group will be

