2.2 Sample Size Determination

During Phase 2b, approximately 160 participants will be enrolled and randomized 1:1:2 to rNAPc2 dose regimen 1, rNAPc2 dose regimen 2, and heparin SoC, respectively. Assuming approximately 20% of participants may not be evaluable for any reason, 160 randomized participants will provide for approximately 130 evaluable participants. At a sample size of 160, the study will have adequate power across a range of clinically meaningful effect sizes, operationalized as proportional reductions in D-dimer (relative to heparin) from 20% to 40% in increments of 5% (see below). This sample size was selected, based on a statistical simulation using Wilcoxon rank sum and assuming a 20% missing/dropout rate, to ensure inferences for the primary endpoint analysis will be robust, given certain potential confounding factors such as missing data (random or non-random), heterogeneous application of heparin (low molecular weight and unfractionated; prophylactic and therapeutic), effects of subject-level covariates (e.g., comorbidities), and effects of site-level covariates (e.g., country).

Power, Primary Endpoint							
	Effect Size (Proportional Reduction)						
	Enrolled Subjects	Evaluable Subjects	20%	25%	30%	35%	40%
Sample Size	80	64	55.8%	67.4%	75.6%	81.0%	84.5%
	100	80	60.5%	72.7%	80.1%	84.9%	87.8%
	110	88	63.6%	76.2%	80.7%	86.6%	89.2%
	120	96	65.2%	78.0%	82.8%	86.9%	91.0%
	130	104	68.2%	79.3%	84.8%	88.7%	91.7%
	140	112	68.9%	80.7%	86.6%	89.3%	92.5%
	160	128	71.3%	83.1%	88.3%	91.3%	94.1%
	180	144	74.9%	84.5%	89.5%	92.5%	94.6%
	200	160	77.2%	86.5%	91.0%	93.8%	95.8%

*Significance via $\alpha = 0.05$
 †Simulated with 20% Missing Data
 ‡Percentages as Averages Across Other Simulation Conditions

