5.3 Subgroups

For the primary efficacy endpoint, the treatment effects across the following subgroup factors will be examined:

- D-dimer randomization stratification factor ($>$ vs. $\leq 2x$ local laboratory ULN)
- Treatment with an agent with demonstrated efficacy in patients with COVID-19, as described in [Section 6.2.1](#) (yes, no)
- Background antiplatelet therapy at baseline, as described in [Section 6.2.1](#)
- rNAPc2 dose regimen
- Initial heparin dosing strategy (prophylactic vs. therapeutic; within regimen comparison only)
- Severity of disease (as defined in [Section 14.1](#))
- Source of Laboratory Values used for primary endpoint determination (central vs. local)

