5.4 Adjustments for Covariates

Where indicated analyses will include a covariate for study stratification ‘D-dimer level at screening’ ($>$ or $\leq 2X$ the assay's ULN).

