7.4 Significance

All statistical tests and confidence intervals will use a 2-sided analysis with a significance level of $\alpha = 0.05$.

8 Safety Analysis

The following safety analyses will be based on the Safety population and on-treatment data scope. Additional safety analyses are detailed in [Section 11.4](#).

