11.1 Primary Efficacy Endpoint Sensitivity Analysis

As a sensitivity analysis, all types of missingness will be addressed via multiple imputation, with a target of 100 multiply imputed datasets. These analyses will be created for findings obtained initially with all available data, with subsequent analysis and pooling performed to evaluate if missing data produces bias in model point estimates or otherwise influences the inferential process.

Multiple imputation will be performed via PROC MI in SAS v9.4. The variables used in the imputation model are the six pre-specified sub-groups of interest, along with any relevant measurements for a subject that will better inform the imputation process (e.g., with missing Day 8 D-dimer, one would include baseline D-dimer in the model). The missing data mechanisms theoretically conferring unbiased estimation (given appropriate covariate selection in the imputation model) using this methodology are MCAR and MAR, although “modern” methodology (MI or FIML [full information maximum likelihood]) also demonstrates superior properties to listwise deletion et al in the MNAR case. Reference Appendices in [Section 14.2](#) which contain descriptions of the Bayesian models, methods for multiple imputation, and methods for power analysis used in this study.

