11.2 Primary Efficacy Endpoint Subgroup Analyses

In order to test for subgroup sensitivities, a Bayesian generalized linear mixed effects model will be constructed. This model will evaluate the influence of pre-specified subgroups of interest, D-dimer stratum, and potential site-level heterogeneity in patient outcomes.

A separate set of analyses for each rNAP2 dosing instance will be constructed, such that the effect on D-dimer of each incremental dose of rNAP2 is estimated. These analyses will therefore be equivalent in

formulation to the Primary Efficacy Analysis as specified above, with estimates of instantaneous treatment effect at Days 3, 5, and 8 for subjects receiving 1, 2 or 3 doses of rNAPc2 or receiving SoC heparin through days 1, 3, and 7, respectively.

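### The protocol lists an analysis of effect by the extent of baseline D-dimer elevation; the available SAP text examines only the two-level screening stratum and does not record the difference

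*SAP*

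**What the plan says.** **Protocol.** Section 9.4.2 commits to a series of secondary analyses of the Phase 2b primary endpoint. One is "effectiveness that is related to the extent of baseline D-dimer elevation". The subgroup analyses of Section 9.4.7 follow as a further item in the same list, and D-dimer is already one of the 9.4.7 factors. Section 9.4.1 lets the SAP prevail where the two documents differ on analysis.

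**SAP.** Section 5.3 lists the "D-dimer randomization stratification factor", which has two levels: above, or at or below, 2x the local laboratory ULN. Section 5.4 uses the same stratum: "Where indicated analyses will include a covariate for study stratification". Section 11.2 plans a Bayesian generalized linear mixed model and names its inputs: "This model will evaluate the influence of pre-specified subgroups of interest, D-dimer stratum, and potential site-level heterogeneity in patient outcomes".

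The D-dimer level itself appears in the endpoint formula (7.1.1), in the baseline summary (6.2) and, as an example, in the imputation model (11.1: "with missing Day 8 D-dimer, one would include baseline D-dimer in the model"). None of these makes it an effect modifier. Section 12 lists four changes from the protocol, and this is not among them.

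**The concern.** Extent of elevation reads most naturally as a graded question. Under a single cut at 2x ULN, a patient at 2.1x and a patient at 20x count as the same, so the analysis cannot show how the effect changes within either side of the cut.

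The stratum also need not come from the same sample as the endpoint baseline. It is a local screening value, for which the admission sample is preferred (Protocol 5.1 and 8.1.2). The endpoint baseline is the Day 1 central value, or a paired local value if the central one is missing (SAP 7.1 and 7.1.1).

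The relation matters because Phase 2b data may lead to adjusted eligibility criteria (Protocol 1.1), and raised D-dimer is the main entry requirement (Protocol 5.5). If the graded analysis is not specified beforehand, any later version of it will be post hoc. The point concerns effect modification, not baseline adjustment of the primary Wilcoxon test.

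**Working it through.** **1. Text.** If the 9.4.2 item meant only the D-dimer subgroup row, it would duplicate the 9.4.7 item beside it. The SAP sections that use D-dimer as a modifier or covariate (5.3, 5.4, 7.2.2, 7.2.3, 11.2) all use the two-level stratum. The mismatch therefore rests on the text alone; steps 2 to 5 only illustrate what it might cost.

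**2. The plan's own figures.** SAP 2.2: "160 randomized participants will provide for approximately 130 evaluable participants", with the table note "Simulated with 20% Missing Data". 160 x 0.80 = 128, as in the table. Allocation of 1:1:2 makes pooled rNAPc2 versus heparin 80 v 80, so 64 v 64 evaluable. SAP 7.4: "All statistical tests and confidence intervals will use a 2-sided analysis with a significance level of" 0.05. The table's 71.3% to 94.1% at 160 enrolled is power for the main effect. It cannot be re-derived, because no SD or simulation conditions are given. No power is stated for an interaction.

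**3. Illustration, linear relation.** Assumptions not in the documents: log baseline is normal, the treatment effect is linear in it, and the stratum is a cut of that same variable. With 64 v 64, the interaction's standard error, in residual SD per baseline SD, is 2/√128 = 0.177. For an interaction g:

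- continuous term: power = Φ(g/0.177 − 1.96)
- two-level term: power = Φ((g/0.177)·√E − 1.96), with E = φ(z_p)²/(p(1−p)) for a cut at percentile p. E is 0.637 at the median and 0.539 at the 25th or 75th percentile.

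| g | Continuous | Two-level, median cut | Two-level, 25th/75th |
|---|---|---|---|
| 0.3 | 40% | 27% | 24% |
| 0.4 | 62% | 44% | 38% |
| 0.5 | 81% | 62% | 55% |
| 0.6 | 92% | 77% | 70% |

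Simulation (2,000 trials per cell, residual SD 0.9, continuous baseline main effect kept in both models) gave:

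| g | Continuous | Two-level, cut at 35th–65th | Two-level, 25th/75th |
|---|---|---|---|
| 0.3 | 36–39% | 25% | 21–22% |
| 0.4 | 59–61% | 38–43% | 34–35% |
| 0.5 | 78–80% | 57–60% | 50% |
| 0.6 | 91–92% | 72–73% | 65–66% |

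The simulated two-level powers are mostly a few points below the formula, which ignores the interaction variance left within each level. The simulated loss is 11 to 29 points.

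**4. Outside that grid.** In further simulations with the cut at the median and at the 25th percentile, the loss was 1–2 points at g = 0.1, about 6 at 0.2, and 6–11 at 0.8. If the screening value correlates only 0.8 with the Day 1 baseline, the loss grows: at g = 0.5 and a median cut, power falls from 77% to 39%.

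**5. Step-shaped effect.** If the effect changes in a step exactly at the cut, the order reverses. Simulated power was 38% (two-level) v 26% (continuous) and 80% v 59% with a median cut, and 30% v 18% and 67% v 39% at the 25th percentile. The formula agrees: where the two-level test has 80% power, the linear term has 61% at a median cut.

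**The case against.** **The protocol does not say continuous.** Above versus at or below 2x ULN is itself a measure of extent, secondary analyses are left to the SAP, and the SAP prevails. This stands as far as it goes: a reader might infer that the protocol requires a continuous model, and it does not. It does list the analysis separately from the subgroups, so the silence in SAP 12 remains a fair documentation point.

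**The SAP may contain the analysis.** A reader might conclude that it has been dropped. That cannot be confirmed. SAP 11.1 says the Section 14.2 appendices describe the Bayesian models, and 14.2.1 has only a heading in this copy. Against this, 11.2 names the model's inputs and gives D-dimer as the stratum.

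**The power figure.** A reader might take 11 to 29 points as a loss this trial will suffer. The documents do not support that. They give no interaction size, D-dimer distribution, share above 2x ULN or effect shape. The lower end comes from starting the grid at 0.3, and the sign reverses for a step at the cut. The 11.2 model is Bayesian with no stated decision rule, so frequentist power is only an analogue.

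**Assay mixing.** Raw log values would combine central and local assays, which the ULN-scaled stratum avoids. This stands, and the remedy has to scale by ULN. A curve in Day 1 values would also not map directly onto eligibility, which is set on the local screening value.

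**Conclusion.** The point holds as a mismatch between protocol and SAP and as an inexpensive improvement; it is not an error in the primary analysis. In the SAP text available, the separately listed analysis by extent of baseline elevation is reduced to the two-level stratum, and the change is not recorded. This is subject to what 14.2.1 may contain.

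No single loss of power follows from the documents. Under a linear relation on the log scale, with 128 evaluable patients and interactions of 0.3 to 0.6 residual SD per baseline SD, the illustrative loss is roughly 10 to 30 points. It is smaller for weaker or stronger interactions. Under a step at 2x ULN the two-level factor is the better test, which is a reason to keep it beside the graded term.

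**What to change.** In SAP 11.2, add a treatment by log(baseline D-dimer) interaction to the planned mixed model. Use the same baseline value as the primary endpoint, expressed as a multiple of the ULN of the assay that produced it (central or local). Report the rNAPc2/heparin ratio with its interval across the observed baseline range, for example at the quartiles. A ratio needs D-dimer on the log scale, which SAP 5.8 already lists as a candidate transformation. Keep the two-level stratum row as a check on a step-shaped effect. State that the curve is in Day 1 values, whereas eligibility uses the local screening value.

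If 14.2.1 already contains such a term, refer to it from 11.2. If the sponsor does not want the analysis, record its omission in SAP 12.

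The cost is one model term and one figure, or one sentence in Section 12. No new patient measurements are needed: percent change already requires a baseline value for every patient in the primary analysis, and the assay ULNs only have to be carried into the analysis data set. The downside is the assumed log-linear shape, which the retained stratum row lets readers check.

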4 STUDY DESIGN

4.1 OVERALL DESIGN

Hypothesis: rNAPc2, a novel, potent and highly selective tissue factor inhibitor with anticoagulant, anti-inflammatory and potential antiviral properties, shortens time to recovery in hospitalized patients with COVID-19.

This protocol describes sequential Phase 2b/3 randomized, active comparator, multicenter superiority studies comparing rNAPc2 to heparin in hospitalized patients with COVID-19 and elevated D-dimer level. The study utilizes a PROBE (Prospective Randomized Open-Label, Blinded End-point) design^{27,28}. Study participants and Clinical Endpoint Committee (CEC) members assessing the clinical endpoints will be blinded to treatment assignment. Randomization will be stratified by the participant's local laboratory D-dimer level at screening (> or ≤ 2X the assay's upper limit of normal (ULN)).

The primary objective of the Phase 2b study is to identify a rNAPc2 dosing regimen with an acceptable bleeding profile and which reduces D-dimer levels compared to SoC heparin regimens. The primary safety endpoint is major or non-major clinically relevant bleeding within 8 days of randomization and the primary efficacy endpoint is change in D-dimer level from Baseline to Day 8, or day of discharge if prior to Day 8. Secondary and exploratory objectives and endpoints are detailed in [Section 3 OBJECTIVES AND ENDPOINTS](#).

During Phase 2b, an interim efficacy analysis will be conducted when 120 participants have completed Day 8 assessments, or Day of Discharge assessments if the participant is discharged prior to Day 8. To account for early recovery, deaths, and lab errors which may lead to lack of Day 8 D-dimer in approximately 20% of patients, 120 participants will provide for approximately 100 participants to be evaluated in the interim efficacy analysis. The interim efficacy analysis will test for futility based on the primary study hypothesis. Additionally, at the interim efficacy analysis, the Data Safety Monitoring Committee will be empowered to adjust sample size as pre-specified in the Phase 2b interim analysis

plan. While this review is taking place, the study will continue to enroll. Upon completion of Phase 2b, the database will be locked for analysis of clinical and biomarker data.

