6.3 Treatment Exposure and Adherence

Treatment exposure and adherence will be summarized by treatment group for the ITT, Per Protocol and Safety population and listed.

7 Efficacy Analysis

The following efficacy analyses will be based on the ITT population and data scope. Accompanying analyses pertaining to mITT and Per Protocol population, subgroup and sensitivity are discussed in [Section 11](#).

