7.2.3 Composite of Clinical Events

The secondary efficacy clinical composite will be measured and compared between treatment groups. This composite will consist of death (all-cause), thrombotic events (Stroke, MI, PE, peripheral arterial and clinically relevant deep vein thrombosis), organ support as defined in [Section 7.3.2](#), and rehospitalizations adjudicated as to its relatedness to COVID-19.

The primary formulation of the composite will limit the number of contributing events per component per patient to one, i.e., the aggregate will have values from 0 – 4 for each patient. The component-wise analysis will be performed using logistic regression, where the contribution of each component is necessarily a dichotomous variable. The aggregate will be analyzed using Poisson regression.

The secondary formulation will differ from the primary in that no limitation on the component-wise contributions will be imposed. Thus, component-wise analysis will also be Poisson regression except in the case of death or any data-driven circumstance where the only available values are binary.

Regression models will include treatment in the unadjusted formulation, and treatment, D-dimer stratum and pre-specified subgroups in the covariate-adjusted formulation. Pre-existing organ support of any modality is discussed below as an additional covariate, representing a special case arising from the specifications of the analysis.

Assumptions inherent to any of these models, e.g., whether data manifest in accordance with a Poisson distribution (where λ , the rate, is both mean and variance) will be tested. In the case of Poisson, testing significant deviations from assumptions will use Likelihood Ratio tests on Zero-inflated and/or Negative Binomial operationalizations of the dependent variable distribution (these are not mutually exclusive). Both Logistic and Poisson regression models may remove variables that introduce issues in the model estimation process, e.g., a regressor with no variance, cell sparsity, or sufficient multicollinearity to induce rank deficiency of the model-implied design matrix will flatten the likelihood function, destabilizing point estimates and inflating confidence intervals by orders of magnitude.

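### Laboratory source of the D-dimer endpoint should not be a covariate in the adjusted composite and component models of SAP 7.2.3: it is fixed after randomization and undefined for patients with no endpoint value, some early deaths among them

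*SAP*

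**What the plan says.** SAP 5.3 gives seven subgroup factors for the primary efficacy endpoint. The last is "Source of Laboratory Values used for primary endpoint determination (central vs. local").

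SAP 7.2.3 sets out two versions of each composite model: "Regression models will include treatment in the unadjusted formulation, and treatment, D-dimer stratum and pre-specified subgroups in the covariate-adjusted formulation". On the components, death being one: "The component-wise analysis will be performed using logistic regression". The aggregate is analysed by Poisson regression. A binary covariate for pre-existing organ support is added.

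On who is analysed, SAP section 7 opens with "The following efficacy analyses will be based on the ITT population and data scope", and SAP section 10 bases net outcomes on everyone randomized, over 30 days.

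On missing D-dimer, Protocol 4.1 expects "early recovery, deaths, and lab errors which may lead to lack of Day 8 D-dimer in approximately 20% of patients". SAP 7.1.1 accepts local-local pairs where central values are unavailable, and samples within 48 hours either side of Day 8 or discharge. SAP 5.1 then allows LOCF from values taken after the final dose. SAP 11.1 adds multiple imputation as a sensitivity analysis, which SAP 7.2.1 and 11.3 extend to secondary endpoints.

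**The concern.** Laboratory source describes how the D-dimer endpoint was obtained. It is not a baseline characteristic. In a model for death or clinical events it raises two problems.

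- **Loss of patients.** With no endpoint value there is no source, and SAP 7.2.3 does not say what happens when a covariate is missing. Standard logistic and Poisson procedures drop such records. Death is a stated reason for a missing Day 8 D-dimer, so the loss depends on the outcome being modelled.
- **Conditioning on a consequence of the outcome.** Where a source is known, it may be local because the patient died before the next scheduled central sample. Adjusting a death model for it conditions on something that death affects, even if nobody is dropped.

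The composite is a secondary efficacy endpoint, non-primary endpoints fall under the multiplicity procedure of SAP 5.7, and the SAP does not say whether the adjusted or the unadjusted result leads.

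**Working it through.** **1. Is laboratory source among the adjustment covariates?** SAP 7.2.3 names the D-dimer stratum separately from the subgroups. So does SAP 11.2: "This model will evaluate the influence of pre-specified subgroups of interest, D-dimer stratum, and potential site-level heterogeneity in patient outcomes". SAP 11.1 gives the count: "The variables used in the imputation model are the six pre-specified sub-groups of interest". The SAP 5.3 list has seven factors; 7 − 1 (D-dimer stratum) = 6, and laboratory source is one of the six. The subgroup list in Protocol 9.4.7 also has seven factors including D-dimer, so the count alone does not decide between the lists. However, SAP 5.6 calls the rNAPc2 dose variable a pre-specified subgroup, and that factor appears only in SAP 5.3. Protocol 9.4.1 also lets the SAP prevail on analysis.

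**2. The plan's own figure.** Evaluable = randomized × (1 − missing share) = 160 × 0.80 = 128, as in the power table (about 130 in the text). Not evaluable: 160 − 128 = 32. This is the ceiling before any fallback.

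**3. What the fallbacks leave.** Protocol Table 2b schedules central D-dimer on Days 1, 2, 3, and 8 or discharge.
- A patient dosed on Day 5 who dies before the Day 8 sample has no later scheduled central D-dimer. Any usable value would normally be local.
- A patient who dies after a single rNAPc2 dose can have the Day 2 central sample, which follows that dose.
- rNAPc2 is dosed on Days 1, 3 and 5, while heparin can continue until death. Values after the final dose may therefore be available unequally by arm. SAP 5.1 does not say whether the final dose means the last planned or the last received.

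**4. Deaths lost.** The documents give no mortality, so both inputs are assumptions. Deaths lost = 160 × m × f, with m the 30-day mortality and f the share of deaths without a usable value. At m = 10% there are 16 deaths:

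| f | Deaths lost | Apparent rate if only these drop |
|---|---|---|
| 10% | 1.6 | 14.4/158.4 = 9.1% |
| 25% | 4 | 12/156 = 7.7% |
| 50% | 8 | 8/152 = 5.3% |

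Over m from 5% to 20% and f from 10% to 50%, the loss runs from 0.8 to 16 deaths.

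A logistic fit on constructed data (160 patients, 16 deaths, 32 missing sources of which 8 were deaths) confirmed the mechanism: the unadjusted model used 160 patients and 16 deaths, the adjusted model 128 and 8.

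**5. Effect on the odds ratio.** If only deaths drop, the odds of death in an arm become m(1 − f)/(1 − m). With no true effect, the apparent OR (rNAPc2 vs heparin) is (1 − f for rNAPc2)/(1 − f for heparin), whatever the mortality. Equal loss gives 1. Losing 10% of rNAPc2 deaths and 25% of heparin deaths gives 0.90/0.75 = 1.20; 10% and 50% gives 0.90/0.50 = 1.80. These are illustrations; the documents do not fix the direction or size.

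**6. Two other factors on the list.** rNAPc2 regimen has no value in the 80 heparin patients, and initial heparin strategy none in the 80 rNAPc2 patients. Entered literally with complete-case fitting, the adjusted model keeps 160 − 80 − 80 = 0 patients.

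**The case against.** A reader might infer that early deaths vanish from the trial's mortality and composite results. The documents do not support that. The unadjusted models contain treatment only and keep everyone. Time to death, and time to death or thrombosis (SAP 7.3.1, by the methods of 7.2.2), use a log-rank test and Cox model stratified by screening D-dimer alone.

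A reader might also take 20% as the share lost, or suppose that half of deaths go. The 20% is a planning allowance that covers early recovery and laboratory errors as well as deaths, and it stands before the fallbacks. Patients discharged early are due a discharge sample, local D-dimers are recorded in hospital, and exclusion criterion 5 removes patients expected to die within 72 hours. Any fraction of deaths lost is an assumption.

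Three further points have force.
- Listwise deletion is a software default, not a rule in the SAP. The SAP itself prefers multiple imputation, and the text available shows only a heading for the imputation appendix (14.2.2), so no claim can be made about what that appendix omits.
- The clause in SAP 7.2.3 on removing troublesome variables gives its reasons as examples, so it could be stretched to missing covariates.
- The SAP 5.3 list is introduced for the primary endpoint and cannot be entered literally (step 6), so some selection is unavoidable.

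These points limit the reach but do not remove the problem. The removal clause is permissive, which would leave the choice of covariates until the data are seen. Imputation is a sensitivity analysis only, and its model uses the same six factors, so it would impute a laboratory source that never existed. Neither answers the objection that a local source can follow from early death.

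**Conclusion.** Wrong as written, but only in the covariate-adjusted composite and component models of SAP 7.2.3; low to moderate severity. The most natural reading of the SAP brings in a post-randomization factor that is undefined without a D-dimer endpoint and may depend on early death. This conflicts with the ITT basis in section 7 and the all-randomized basis in section 10.

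The ceiling is 32 of 160 patients before any fallback. The number of deaths lost is unknown: about 2 to 8 of 16 if mortality is 10% and 10% to 50% of deaths lack a usable value, both assumptions. The loss also presumes default complete-case fitting. Equal loss in the two arms would distort the event rate more than the odds ratio; unequal loss could create an apparent effect. How much this matters depends on which formulation leads, and the SAP leaves that open.

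**What to change.** In SAP 7.2.3, replace the reference to pre-specified subgroups with a named list of covariates known at baseline for every patient: D-dimer stratum, baseline disease severity, baseline antiplatelet therapy and pre-existing organ support. Treatment with a proven COVID-19 agent qualifies only if defined as given before randomization, since SAP 6.2.1 covers both periods.

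- State that laboratory source is not a covariate in these models, nor in the imputation model of SAP 11.1.
- Leave out rNAPc2 regimen and initial heparin strategy as covariates, because each is undefined in the other arm.
- State whether the adjusted or unadjusted formulation leads, and how any missing baseline covariate is handled.
- Keep laboratory source as a subgroup or sensitivity analysis of the D-dimer endpoint, for example by repeating the primary test in central-central pairs.

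The time-to-event analyses need no change. The cost is a few sentences in the SAP, with no new data and no change to sample size or conduct.
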